#### **11.10. Analysis of safety data**

The analysis of the safety variables will be based on the safety analysis set.

##### **11.10.1. Adverse events**

All AEs will be coded using MedDRA, and will be listed for each subject. A treatment-emergent adverse event (TEAE) is defined as an AE with onset (start date/time) after the first dose of IMP in Treatment period 1. Adverse events will be assigned to a treatment based on the start date/time of the AE:

- Screening: all AEs with start date/time prior to dosing in Treatment period 1.

- Treatment period 1: AEs with start date/time at the time of or after dosing in Treatment period 1 until the time of dosing in Treatment period 2.
- Treatment period 2: AEs with start date/time at the time of or after dosing in Treatment period 2 until the time of dosing in Treatment period 3.
- Treatment period 3: AEs with start date/time at the time of or after dosing in Treatment period 3 until the time of dosing in Treatment period 4,
- Treatment period 4: AEs with start date/time at the time of or after dosing in Treatment period 4 until the final follow-up visit.

Adverse events with missing start dates/times will be handled as follows:

- If the start date is completely missing but the end date is known and shows that the AE ended on or after the first dose date, then the start date will be imputed as the first day of dosing; if the end date is known and shows that the AE ended before the first dose date, then the screening date will be used for the start date. If the end date is non-informative (i.e., is missing or does not contain enough information), the start date will be imputed as the first date of dosing;
- If only the start day is missing the day will be imputed as the first day on which a dose was given in that month unless the end date is known and shows that the AE ended before a dose was given in that month; in which case the date will be imputed as 01. If the end date is non-informative (i.e., is missing or does not contain enough information), the start date will be imputed as the first date of dosing in the known month. If the month is not a dosing month the date will be imputed as 01;
- If the start day and month are missing the date will be imputed as the first day of dosing in the known year unless the end date is known and shows that the AE ended before a dose was given in that year; in which case the start day and month will be imputed as 01Jan or with the date of Screening if this is later. If the end date is non-informative (i.e., is missing or does not contain enough information), the start date will be imputed as the first date of dosing in the known year. If the year is not a year of dosing then the date will be imputed as 01Jan or with the date of Screening if this is later.
- Missing times will be imputed as 00:00 h or with the time of dosing for events starting on a dosing day.

Adverse events will be summarized by treatment (where treatments will be pooled across the treatment periods) and overall, including tabulations by causality and severity (mild, moderate and severe). All tabulations will be presented by SOC and PT. Furthermore, listings of SAEs and AEs that led to withdrawal will be made and the number of subjects who

had any AEs, SAEs and AEs that led to discontinuation will be summarized. The AEs that occur before (first) dosing will be excluded from the summary tables.

The following information will be included in the listings: verbatim term, MedDRA SOC, PT and lowest level term, start date/time, end date/time, time from last dose, causality, action taken, whether the AE was classified as serious and the outcome.

All tabulations will include the number and percentage of subjects.

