-  Ambulatory visits: Screening and Day 4 to each treatment period, and final follow-up/early termination (ET) visit\*\*.
-  IMP administration: On Day 1 at 0 hours to each treatment period.
-  Questioning will be conducted spontaneously plus at the following scheduled time-points to each treatment period: pre-dose (0 hours) and post-dose at 3, 12, 24 and 48 hours. Serious adverse events (SAEs) will be recorded from the signing of informed consent and adverse events (AEs) will be recorded from randomization until the final follow-up/ET visit. Data to be collected for statistical analysis are described in [Section 11.10.1](#).
-  Blood pressure (BP) and pulse measurements (supine position) will be collected at screening and for each treatment period on admission, at pre-dose (0 hours) and post-dose at 24 and 48 hours, as well as at the final follow-up/ET visit.
-  12-Lead electrocardiogram (ECG) will be performed at screening, first admission to the clinical unit (Visit 2, Day -1), 1.25 hours after each dose (Visits 2-5, Day 1), as well as at the final follow-up/ET visit (total of 7 ECGs per subject who complete the study).
-  Hematology, clinical chemistry and urinalysis will be performed at screening and at the final follow-up/ET visit; in addition, for the first and third treatment period at pre-dose.
-  Serum pregnancy test at screening; urine pregnancy tests thereafter (females only).
-  Full physical examination will be performed at screening and the final follow-up/ET visit. Abbreviated physical examination will be performed on admission and at 48-hours post-dose to each treatment period.
-  C-SSRS will be performed at screening (version Baseline - Screening) and at the final follow-up/ET visit (version Since Last Visit) (see [Appendix 15.5](#)).
-  Prior and concomitant medications are defined, and data to be collected for statistical analysis are described in [Section 11.8.1](#).
-  Blood samples for the determination of plasma concentrations of naloxegol will be collected for all treatment periods at the following time-points: pre-dose (0 hours [within 30 minutes prior to IMP administration]) and post-dose at 0.25 (15 minutes), 0.5 (30 minutes), 1, 1.5, 2, 3, 4, 5, 6, 8, 10, 12, 16, 24, 36, 48 and 72 hours (18 samples per treatment period).

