### **8.8. Treatment compliance**

Administration of IMP will take place at the PAREXEL Early Phase Clinical Unit. Data will be captured in ClinBase.

For Treatment A, C and D, the exact day and time of IMP administration will be recorded. A check of the subject's mouth and hands will be performed after dosing.

For Treatment B, the time at which the IMP is fully administered into the nasogastric tube will be taken as the time of dosing, for calculation of PK parameters. The exact day and time of IMP administration will be recorded.

Further data on dispensing and IMP administration to be captured in ClinBase, e.g., volume administered, will be detailed in the dispensing and handling instructions, which will be provided separately from this protocol.

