#### **12.2.4. Causality collection**

The investigator will assess causal relationship between IMP and each AE, and answer “yes” or “no” to the question: *“Do you consider that there is a reasonable possibility that the event may have been caused by the investigational product?”*

For SAEs causal relationship will also be assessed for study procedures. Note that for SAEs that could be associated with any study procedure the causal relationship is implied as “yes”.

A guide to the interpretation of the causality question is found in [Appendix 15.1](#) of this clinical study protocol.

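### Adverse events starting at nasogastric tube insertion are tabulated under the treatment given before Treatment B, or left out of the tables, rather than under B

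*Protocol*

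**What the plan says.** Section 11.10.1 of the protocol allocates AEs by start date and time, and each window opens at one dose and closes at the next:

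- Before the first dose: "Screening: all AEs with start date/time prior to dosing in Treatment period 1".
- From the first dose: "AEs with start date/time at the time of or after dosing in Treatment period 1 until the time of dosing in Treatment period 2".
- From the second dose: "AEs with start date/time at the time of or after dosing in Treatment period 2 until the time of dosing in Treatment period 3".
- From the third dose: "AEs with start date/time at the time of or after dosing in Treatment period 3 until the time of dosing in Treatment period 4".

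The period 4 window runs from its dose to final follow-up. Summaries are by treatment, pooled over periods, and "The AEs that occur before (first) dosing will be excluded from the summary tables". All AEs are listed.

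For Treatment B, section 8.8 says that "the time at which the IMP is fully administered into the nasogastric tube will be taken as the time of dosing", and the same sentence limits this convention to calculating PK parameters. On procedures, section 12.2.4 says: "For SAEs causal relationship will also be assessed for study procedures". For other AEs only causality against the investigational product is collected (section 12.2.3).

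Section 11.1 states that no separate statistical analysis plan will be written, apart from a possible abbreviated one for changes. Section 11.10.1 is therefore the operative rule.

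**The concern.** Treatment B is the only treatment with a procedure that comes before the dose. Events that insertion could plausibly cause, such as gagging, nasal pain or a nosebleed, would start before the B dose. A rule that switches treatment only at the moment of dosing cannot credit them to B.

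These events would be captured. Section 12.2.1 collects AEs from randomization, which takes place on Day -1 of period 1, and footnote 7 of Table 1 schedules AE questioning before the dose in every period. Inclusion criterion 3 checks tube tolerance only by asking the subject, so intolerance may first show at insertion. If a subject withdrew at that point in periods 2 to 4, the event would be set against the preceding treatment.

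At stake are the by-treatment AE tables that serve the secondary safety and tolerability objective, in a study meant to inform which alternative routes can be used. The error has a direction: it lowers the count for the tube route and raises the counts for the reference and the other two test treatments.

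**Working it through.** The plan states no expected AE figure, so there is none to reproduce. The check is to trace where the rule sends an event.

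**Inputs**

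- Sequences ADBC, BACD, CBDA and DCAB, and up to 44 subjects (section 11.4).
- Assignment windows and the exclusion of AEs before the first dose (section 11.10.1).
- Equal allocation to the four sequences is assumed: 44 / 4 = 11 each.
- Insertion precedes administration. The protocol does not say by how long, but a tube must be placed before it is used.

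**Destination of an event with a recorded onset at insertion**

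| Sequence | Period of B | Window containing the event | Tabulated under | Subjects |
|---|---|---|---|---|
| ADBC | 3 | period 2 | D (reference) | 11 |
| BACD | 1 | before first dose | Screening, not summarized | 11 |
| CBDA | 2 | period 1 | C | 11 |
| DCAB | 4 | period 3 | A | 11 |

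So insertion events from 11 + 11 + 11 = 33 subjects go to another treatment, those from 11 stay out of the tables, and those from 0 of 44 go to B. With the 36 evaluable subjects the split is 9, 9, 9 and 9, again with none to B. This pattern holds whatever the event rate.

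**Exception.** Section 11.10.1 allows a missing time on a dosing day to be imputed as the time of dosing. That would move an insertion event to B. A recorded time is never moved.

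**Scale, illustration only.** The protocol gives no rate of insertion events. Let p be the proportion of B administrations with a recorded event at insertion. B then loses 44 × p subjects with an event. A, C and D each gain up to 11 × p, or 11 × p / 44 = p / 4 as a proportion of subjects.

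| Assumed p | Lost from B | Gained by each of A, C, D | Added to each rate |
|---|---|---|---|
| 5% | 2.2 | 0.55 | 1.25 points |
| 20% | 8.8 | 2.2 | 5 points |
| 30% | 13.2 | 3.3 | 7.5 points |
| 40% | 17.6 | 4.4 | 10 points |

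These values of p are assumptions chosen to show a range, not estimates.

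**Plausibility of the attribution.** The washout is at least 7 days (section 7.1), or 7 × 24 = 168 hours. The stated half-life is 6 to 11 hours (section 5.4.4). At insertion, at least 168 / 11 = 15 half-lives have passed since the treatment to which the event is booked.

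**The case against.** The strongest defence is that the secondary objective concerns single doses of naloxegol, not the tube. An event before the B dose cannot be caused by that dose, and assigning events to the latest dose is a coherent convention. This stands as a reason not to call insertion events drug reactions. It does not justify counting them under A, C or D, which were given at least a week earlier.

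There is also a partial safeguard. Every AE carries a causality rating against the product, and the tables are broken down by causality. Insertion events judged unrelated would inflate the all-AE counts but not the drug-related ones. That stands and limits the harm.

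Four stronger readings are tempting, but the protocol does not support them:

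- *Events in BACD are lost.* They leave the summary tables only; section 11.10.1 lists every AE.
- *Events during tube administration are certainly misassigned too.* Section 8.8 sets the end-of-administration time for PK, and section 11.10.1 does not adopt it for AEs. This is an ambiguity to settle, not a demonstrated error.
- *Non-serious tube events cannot be identified later.* The planned listings give the verbatim term, start time and time from last dose, and section 11.8.2 lists dosing times. A nosebleed just before a B dose could be found. What is missing is a recorded judgement on procedure causality.
- *B is credited with no tube events at all.* Tube events that start after dosing are correctly counted under B.

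**Conclusion.** The rule is wrong as written for one class of event. An AE with a recorded onset at tube insertion is tabulated under D, C or A, or in BACD left out of the summaries, and not under B. This follows from the assignment windows and the sequences, and needs only that insertion precedes the dose. The 11-subject counts further assume equal allocation of 44 subjects.

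The direction is certain wherever such events occur: B is understated, and A, C and D are inflated. The size cannot be estimated from the protocol. The effect is confined to descriptive AE tables; the primary bioavailability comparison is untouched. A reader might infer that the safety comparison is unusable, but the listings and the causality breakdown do not support that. Severity is minor to moderate.

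**What to change.** In section 11.10.1:

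1. Assign AEs with onset from the start of tube insertion in a Treatment B period to Treatment B, flagged as pre-dose/procedure. State that this also covers BACD, where B comes first, so that these events appear in the tables.
2. State which Treatment B time counts as dosing for AE assignment, because section 8.8 defines one only for PK.

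Optionally, in section 12.2.4, record study-procedure causality (yes or no) for all AEs rather than serious ones only. This is best settled before the first dose, since the judgement is harder to make reliably afterwards.

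The cost is a few sentences of protocol text and minor table programming, plus one extra AE field if the option is taken. The start of tube insertion must be recorded if the handling instructions do not already provide for it. No visits or procedures are added for subjects.

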#### **12.2.5. Adverse events based on signs and symptoms**

All AEs spontaneously reported by the subject or reported in response to the open question from the study personnel: *“Have you had any health problems since you were last asked?”*, or revealed by observation will be collected and recorded in ClinBase.

When collecting AEs the recording of diagnoses is preferred (when possible) to recording a list of symptoms and signs. However, if a diagnosis is known and there are other symptoms or signs that are not generally part of the diagnosis, the diagnosis and each symptom or sign will be recorded separately.

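### The rule for missing adverse event start dates in Section 11.10.1 picks the first dose, which in a four-period crossover puts most fully undated events, and about half of month-only events, under the wrong treatment

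*Protocol*

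**What the plan says.** Section 11.10.1 of the protocol sets the allocation rule: "Adverse events will be assigned to a treatment based on the start date/time of the AE". Each period runs from its own dose to the next dose; the fourth runs to final follow-up.

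The same section then fills in missing start dates:

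- Date wholly missing, event ended on or after the first dose: "then the start date will be imputed as the first day of dosing". If the end date is uninformative, again "the start date will be imputed as the first date of dosing".
- Only the day missing: "the day will be imputed as the first day on which a dose was given in that month".
- Day and month missing: "the date will be imputed as the first day of dosing in the known year".
- Time missing on a dosing day: the dosing time, so an imputed event falls in the period which that dose opens.

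The exceptions cover events known to have ended before dosing (overall, in that month or in that year) and months or years without a dose. The output is by treatment: "Adverse events will be summarized by treatment (where treatments will be pooled across the treatment periods) and overall".

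Section 11.1 says that no separate statistical analysis plan will be written, although an abbreviated one may record changes. Section 11.10.1 is therefore the working specification.

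**The concern.** Imputing to the first dose is a cautious convention when a subject receives one treatment: it makes an undated event count as treatment-emergent and does nothing else. Here the sequences are ADBC, BACD, CBDA and DCAB, so the imputed date also selects one of four treatments. The end date is compared only with the first dose overall, in the month or in the year. It is never used to choose among Periods 2 to 4. An undated event that arises and resolves after the fourth dose is tabulated under the first treatment, and its listed time from last dose is wrong as well.

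The tables by treatment, causality and severity serve the secondary objective on safety and tolerability. Events belonging to one method of administration could appear under another, which blurs any difference between methods.

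**Working it through.** The protocol gives no figure for this rule, so there is none to reproduce. The check applies the rule as written, for events that start after a dose and meet none of the exceptions.

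**Inputs.** Four periods with four different treatments (Section 7.2). Washout of at least 7 calendar days between periods (Section 7.1). Screening of at most 28 days and follow-up within 72 hours of the last procedure (Section 7.1). About 9 weeks per subject (Section 7.1.3). Last pharmacokinetic sample at 72 hours (Section 9.2.1). Assumed: equal expected numbers of events per period, equal dose spacing, and a first dose on any day of the year.

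**Plausible dose spacing.** 9 weeks = 63 days. Taking off 28 for screening, 3 for the last sample and 0 to 3 for follow-up leaves 29 to 32 days for three intervals, or 9.7 to 10.7 days each. The shortest spacing considered is 7 days.

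**Date wholly missing.** All events go to Period 1. Share wrong = 1 − share truly in Period 1 = 1 − 0.25 = 75%. If 40% of events truly arose in Period 1 it is 60%; if 50% did, it is 50%.

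**Day and month missing.** If all of a subject's doses fall in one calendar year the answer is again 75%. Averaged over every possible start day, including courses that cross New Year, it is 72% to 74%.

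**Only the day missing.** Take an event with onset in the same month as its dose. It is placed correctly only if that dose is the first of the month. The number of correct periods therefore equals the number of calendar months that contain a dose, which is 1 plus the number of month boundaries between first and last dose. With spacing s, the expected number of boundaries is 3s / (365/12) = 3s / 30.42. So

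share wrong = 1 − (1 + 3s/30.42)/4 = 0.75 − 0.25 × 3s/30.42.

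Day-by-day enumeration over a year, with onset either within 3 days of dosing or spread evenly over the period, agrees:

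| Spacing | Formula | Enumeration |
|---|---|---|
| 7 days | 0.75 − 0.25 × 0.690 = 57.7% | 57.7% to 58.2% |
| 10 days | 0.75 − 0.25 × 0.986 = 50.3% | 50.3% to 52.0% |
| 11 days | 0.75 − 0.25 × 1.085 = 47.9% | 47.9% to 49.9% |
| 14 days | 0.75 − 0.25 × 1.381 = 40.5% | 40.5% to 43.8% |

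**Effect on the tables.** Period 1 contains A, B, C and D once each across the four sequences, so misplaced events spread about evenly over treatments. If a share m of events is fully undated, the tabulated rate is (1 − m) × true rate + m × mean rate, and every difference shrinks by the factor (1 − m). The protocol gives no value for m. For illustration, assume 20% for one treatment and 10% for the other three, so the mean is 12.5%:

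- m = 5%: 19.625% against 10.125%, a difference of 9.5 points
- m = 10%: 19.25% against 10.25%, a difference of 9.0 points
- m = 20%: 18.5% against 10.5%, a difference of 8.0 points

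With 44 subjects per treatment, the losses of 0.5 and 2.0 points are 0.005 × 44 = 0.22 and 0.02 × 44 = 0.88 of a subject.

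**The case against.** The strongest reply is that the rule will seldom be used. Subjects are resident until 48 hours after each dose and are questioned before dosing and at 3, 12, 24 and 48 hours. Start and stop dates and times are collected for every event (Section 12.2.3), and data queries are repeated until resolved (Section 10.5). A wholly missing or year-only date is hard to imagine in that setting. The likelier gap is a missing time, and on a dosing day the stated rule handles that sensibly. No test on AEs is planned, and the listings let a reader check an individual event. All of this stands. It limits the impact but does not make the rule suit a crossover.

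Three stronger readings are tempting, and the documents support none of them:

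- A reader might infer that most undated events of every kind are misplaced. For month-only dates that is clear only near the 7-day minimum. At about 10 days, the spacing that best fits 9 weeks, it is about half, and at longer spacing it is fewer.
- A reader might infer bias towards one treatment. Period 1 is balanced over the four treatments, so the expected effect is dilution.
- A reader might infer that the study already holds a bound on every onset, because subjects are asked "Have you had any health problems since you were last asked". The AE variables in Section 12.2.3 include no date or visit of first report, and nothing says that absence of an event is recorded at each questioning.

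It can also be said that Section 11.1 lets the analysis be changed later. It does, but choosing a different allocation once events are known in an open-label study is weaker than stating it beforehand.

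**Conclusion.** The point holds for the rule as written. No other section of the protocol corrects the choice among Periods 2 to 4. The 75% for fully undated events rests on equal event frequency across periods and stays above one half unless at least half of the events truly arise in Period 1. The month-only figures rest also on equal spacing and an arbitrary calendar start. The practical size depends on how many events lack a start date, which cannot be known from the protocol and is probably small. This is a cheap correction to a secondary, descriptive output and does not threaten the trial's main conclusion.

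**What to change.** Amend Section 11.10.1 so that two decisions are made separately when a start date is missing or partial.

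1. Treatment emergence: keep the present comparison with the first dose. The definition requires onset after the first dose, while an imputed onset equals the dosing time, so the wording should be aligned.
2. Treatment: assign the latest dose given on or before the earlier of the known end date and the date or visit at which the event was first recorded in ClinBase, consistent with any known part of the start date. Fall back to the first-dose rule only when neither bound exists.

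An event that starts and is recorded, or ends, within one period is then placed correctly.

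The cost is one paragraph of text, some programming, and carrying the date or visit of first recording into the AE dataset. Since Section 12.2.3 does not list that item, its availability must be confirmed first. The downside is that late-reported or long-lasting events with a missing start may be assigned to too late a period. The documents do not allow that remaining error to be quantified.
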